## Secondary outcome variable(s)

Quality of life

### Background

Circadian rhythm disorders (CRDs) are a specific cluster of neuropsychiatric symptoms that occur in over 60 percent of patients with dementia and are associated with increased morbidity and mortality and poor quality of life.(1,2) CRD symptoms include late afternoon/evening agitation (e.g., sundowning) and irregular sleep-wake rhythms such as daytime hypersomnia, frequent night wakenings and poor sleep efficiency (3,4) CRD symptoms place a tremendous burden on family caregivers, and are the leading causes of distress, poor quality of life (QOL), and institutionalization in this growing population.(5) Most nonpharmacologic trials for CRD symptoms to date have focused on the administration of artificial indoor light because bright light is the strongest entraining agent for the circadian clock.. While these studies have demonstrated modest improvements in CRD symptoms in otherwise healthy adults(6), they are poorly tolerated in persons with dementia (PWD) (7). Scheduled activity for PWD is shown to be important in reducing neuropsychiatric behaviors and improving QOL but its optimal therapeutic use including the timing and structure of various types of activities remains unknown.. A growing body of research supports the importance of activity-based interventions as a palliative approach to reduce the frequency and intensity of CRD symptoms, enhance personhood and dignity, and improve QOL (8). To date, there are no trials linking the nature and timing of activities with key palliative and biobehavioral outcomes. Scheduling activities based on shifting diurnal patterns across the day such as using cognitively stimulating activities in the mid-morning hours, physically stimulating activities in the afternoon hours and relaxing activities in the evening hours may help to reduce CRD symptoms. In this R01 application we describe a palliative approach that will address these gaps and systematically expand upon our pilot findings. We plan to test the efficacy of a timed and planned activity intervention (Healthy Patterns) designed to improve CRDs symptoms and QOL, and to determine the underlying mechanisms by which the intervention achieves its benefits. 1 Ancoli-Israel S, Klauber MR, Jones DW, Kripke DF, Martin J, Mason W, Pat-Horenczyk R, Fell R. (1997). Variations in circadian rhythms of activity, sleep, and light exposure related to dementia in nursing-home patients. *Sleep*. Jan; 20(1):18-23. 2 Peters ME, Schwartz S, Han D, Rabins PV, Steinberg M, Tschanz JT, Lyketsos CG. (2015) Neuropsychiatric symptoms as predictors of progression to severe Alzheimer's dementia and death: The Cache County Dementia Progression Study. *American Journal of Psychiatry*. Jan 13:appiajp201414040480. 3 Zee, P.C., Vitiello, M. (2009). Circadian Rhythm Sleep Disorder: Irregular sleep wake rhythm type. *Sleep Med Clin*. 4(2): 213218. 4 Sack RL, Auckley D, Auger RR, Carskadon MA, Wright KP Jr, Vitiello MV, Zhdanova IV (2007) Circadian rhythm sleep disorders: part II, advanced sleep phase disorder, delayed sleep phase disorder, free-running disorder, and irregular sleep-wake rhythm. An American Academy of Sleep Medicine review. *Sleep*. 30(11):1484-501. 5 Rose KM, Beck C, Tsai PF, Liem PH, Davila DG, Kleban M, Gooneratne NS, Kalra G, Richards KC.(2011). Sleep disturbances and nocturnal agitation behaviors in older adults with dementia. *Sleep*. Jun 1;34 (6):779-86. 6 Mishima, K., Okawa, M., Hozumi, S., Hishikawa, Y. (2000). Supplemental administration of artificial bright light and melatonin as potent treatment for disorganized circadian rest-activity and dysfunctional autonomic and neuroendocrine systems in institutionalized demented elderly persons. *Chronobiology International* 17(3):419-432. 7 Riemersma-van der Lek RF, Swaab DF, Twisk J, Hol EM, Hoogendoijk WJ, Van Someren EJ.(2008).Effect of bright light and melatonin on cognitive and noncognitive function in elderly residents of group care facilities: a randomized controlled trial. *JAMA* ;299 (22): 264255. 8 Gitlin, L.N., Hodgson, N.A., & Choi, S. (2016, In press). Home-based interventions targeting persons with dementia: What is the evidence and where do we go from here?

### Study Design

#### Phase\*

Phase III

#### Design

We propose a prospective, single blind, two group, randomized trial to test whether the Healthy Patterns intervention improves symptoms of sleep (CRD symptoms) and QOL compared to an attention control condition and to investigate the mechanisms by which CRD symptoms are influenced by the intervention.

### **Study duration**

The study is estimated to begin in June 2016 and end in May 2021. Each participant will be enrolled in the study for 4 months.

### **Resources necessary for human research protection**

Describe research staff and justify that the staff are adequate in number and qualifications to conduct the research. Describe how you will ensure that all staff assisting with the research are adequately informed about the protocol and their research related duties. Please allow adequate time for the researchers to conduct and complete the research. Please confirm that there are adequate facilities for the research.

## **Characteristics of the Study Population**

### **Target population**

Participants will be 200 male and female individuals 60 years of age or older who have been diagnosed with probable dementia (PWD) and their primary caregiver (CG). All will live in the Philadelphia, PA, metropolitan area. We estimate that 51% of participants will be women and approximately one fifth will be African-American.

### **Subjects enrolled by Penn Researchers**

200

### **Subjects enrolled by Collaborating Researchers**

0

### **Accrual**

Our primary recruitment strategy involves identifying potential study participants from three possible sources: 1) A subject registry, which contains names of over 1000 individuals with dementia and their caregivers who participated in the study teams previous studies and have indicated a willingness to be contacted for future studies via Penn Seek; 2) the Penn Memory Center, and 3) mailings to families through over 50 community-based programs and clinical services in the Philadelphia region serving cognitively frail individuals and with whom the study team has a recruitment partnership, 4) utilization of social media, for example, Facebook and Twitter, and 5) iConnect to increase low recruitment numbers.

### **Key inclusion criteria**

Inclusion criteria for PWD: (1) be over age 60; (2) English speaking; (3) be able to tolerate wrist actigraphy; (4) diagnosed with dementia using standard assessments and diagnostic criteria; (5) has CG reporting the presence of CRD symptoms (e.g. symptoms on). If the PWD is on any of four classes of psychotropic medications (antidepressant, benzodiazepines, antipsychotic, or anti-convulsant) or an anti-dementia medication (memantine or a cholinesterase inhibitor), we will require that he/she have been on a stable dose for 90 days prior to enrollment (typical time frame in clinical trials) to minimize possible confounding effects of concomitant medications

### **Key exclusion criteria**

Exclusion criteria for PWD: (1) deemed to be in a crisis/unsafe situation at baseline, (2) reported planned transition to another residential or care setting in less than 6 months, (3) at end-stage disease (defined as bed-bound and non-communicative, or on hospice at baseline), (4) currently enrolled in a interventional clinical trial for dementia or associated symptoms (5) regular use of medications with substantial known effects on the measurement of HPA activity (e.g. corticosteroids, interferons, beta-blockers, cytotoxic chemotherapy); major surgery in the past 3 months; history of major psychiatric and/or personality disorder; history of heavy cigarette smoking (e.g. than 50 pack years); loss of a loved one in the past 3 months. (6) conditions known to affect measurement of circadian rhythm such as use of sedatives/ hypnotics, Huntingtons disease, Cushings disease, Addisons disease, normal pressure hydrocephalus, Parkinsons disease, advanced heart failure (New York Heart Stage 3-4), morbid obesity (BMI 35)

## Vulnerable Populations

### Children Form

**Pregnant women (if the study procedures may affect the condition of the pregnant woman or fetus) Form**

### Fetuses and/or Neonates Form

### Prisoners Form

### Other

**None of the above populations are included in the research study**

## The following documents are currently attached to this item:

*There are no documents attached for this item.*

### Populations vulnerable to undue influence or coercion

Primary participants and their study partners will receive an explicit assessment of capacity consisting of questions related to their understanding of the purpose of the study, the benefits, the risks of the study, and if they are able to withdraw at any time. Due to the progressive nature of dementia and Alzheimer's disease, it is not expected that participants will regain capacity for informed consent over the course of the study if they lack capacity at the initial visit. It's possible that participants may lose consent capacity. At the beginning of each followup visit, the study team will remind the primary participant and study partner/caregiver of the goals of the study, the procedures, benefits, risks, and that they are able to withdraw at any time. If consent capacity has changed, the consent designee will delay further data collection until the appropriate consent procedures have been done. The consent /assent procedures will follow the same steps as described below (In CONSENT SECTION) and the LAR will be asked to consent on behalf of the persons with dementia.

### Subject recruitment

Our primary recruitment strategy involves identifying potential study participants from three possible sources: 1) A subject registry, which contains names of over 1000 individuals with dementia and their caregivers who participated in the study teams previous studies and have indicated a willingness to be contacted for future studies; 2) the Penn Memory Center, and 3) mailings to families through over 50 community-based programs and clinical services in the Philadelphia region serving cognitively frail individuals including PennSeek and with whom the study team has a recruitment partnership, and 4) utilization of social media, for example, Facebook and Twitter, to increase low recruitment numbers. The flyers/letters will have contact information for interested patients to contact the research staff. Flyers/letters will not refer to any disease or condition. Once an interested patient contacts the research staff, the research staff will call interested potential participants. Research staff will not obtain names of potential participants or their contact information until they have expressed a willingness to participate. Research staff will NOT mail or recruit patients who have opted out of research. The penndatastore excludes all patients that have chosen to make use of the opt out flag for research recruitment so study team will not be able to access anyone who has opted out in the reports that are run. Persons screened potentially eligible by telephone and willing to participate will then be scheduled to receive a home assessment and consent visit by [name] or study nurse within a 10 day window and who will conduct a structured and standard clinical examination to: 1) obtain history of cognitive function and cognitive decline, pattern of losses, behavioral changes, and current functioning; 2) substantiate dementia diagnosis and disease stage using standardized mental, general physical, and neurological examinations including the Clinical Dementia Rating Scale (CDR-0.5=very mild dementia; CDR-1=mild; CDR-2=moderate; CDR-3=severe), 3) obtain medical history, co-morbidities, and medication use; and 4) established presence of sleep disturbance.

Will the recruitment plan propose to use any Penn media services (communications, marketing, etc.) for outreach via social media avenues (examples include: Facebook, Twitter, blogging, texting, etc.) or does the study team plan to directly use social media to recruit for the research?

No

## The following documents are currently attached to this item:

*There are no documents attached for this item.*

**Subject compensation\***

Will subjects be financially compensated for their participation?

Yes

**The following documents are currently attached to this item:**

*There are no documents attached for this item.*

**If there is subject compensation, provide the schedule for compensation per study visit or session and total amount for entire participation, either as text or separate document**

Subjects will receive \$100 gift card at the completion of the study.

## **Study Procedures**

**Suicidal Ideation and Behavior**

Does this research qualify as a clinical investigation that will utilize a test article (ie- drug or biological) which may carry a potential for central nervous system (CNS) effect(s)?

No

**Procedures**

The proposed study is a prospective, single blind, two group randomized trial to test whether a timed activity intervention improves symptoms of CRD compared to an attention control condition and to investigate the mechanisms by which CRDs are influenced by a timed activity intervention. Interested CGs who contact the research team will be screened for eligibility by telephone. Those initially eligible and willing, will receive a clinician assessment to obtain written informed consent and to rule out primary sleep disorders requiring specialty care. Once eligibility is determined dyads will receive a baseline home interview (T1). Following the baseline interview, participants will be randomly assigned to experimental or attention-control group conditions and will be contacted to be informed of their respective group assignment within 48 hours of randomization. Experimental dyads will receive up to 8 contacts with a trained nurse interventionist over 1-month. The attention-control group dyads will receive comparable attention in a structured program involving the same number and mix of in-home and telephone contact as the treatment group. All dyads will be retested at 1-month from baseline (T2) to evaluate proximal outcomes of CRD symptoms, QoL, and CG sleep quality; and at 4 months to evaluate distal outcomes including QoL and other measures of satisfaction with the study procedures. Outcome measures will be assessed by interviewers masked to treatment assignment. Timed Activity Intervention Protocol: The timed activity group will involve 4 in-home visits in the mid morning and up to 4 brief telephone education sessions in the evening provided over 4 weeks. The timed activity intervention provides activities delivered at specific times in the daily cycle; it is theory-based, its components have been tested in pilot work; and it is portable and replicable (e.g., protocols are manualized). As in the pilot studies, the in-home sessions are spaced weekly so that the participants can have the opportunity to practice the activity with the interventionist and then on their own. During each session the interventionist will reinforce activity use, review problem solving approaches and provide education. In Session 1 (home visit), the interventionist will explain the nature of the visit and assess the health and functional status and preferences/interests of the PwAD. The interventionist will then provide a suggested morning activity that will match the functional capabilities and interests of the PwAD i.e., based on repetitive motion (e.g., folding towels; sorting objects) and integrating multi-sensory stimulation (photos of interest, objects pleasant to touch). Activities selected are simplified (1 to 2 steps vs. multiple, complex steps), to minimize errors. In Session 2 a follow up phone call will be provided on the following evening to provide coaching in the morning activity. In Session 3 (home visit) the interventionist will review the implementation of morning activities and provide training materials for the evening relaxation protocol. The evening relaxation protocol is a brief 10-step reflexology intervention in which pressure is applied to each of the reflex points on the feet for 30 seconds at a time for a total of 10 minutes. The protocol sequence is based on best practice guidelines. CG are provided a flip book and a CD-ROM demonstrating the procedure and developed in our pilot stud. In Sessions 4-5 (one home visit and one phone call), the interventionist will review integration of

morning and evening activities into daily schedule and will provide written instruction on environmental cues to promote activity and sleep. Session 6 (home visit) is a final review session and wrap up. Attention-Control Condition: The attention control group protocol will be delivered by trained RAs who will provide social attention, empathy and engagement similar in duration to that provided to the Timed Activity Intervention group. The length of time spent will be comparable to the length of time spent in the treatment arm, however this condition will contain no active elements beyond its nonspecific components, and no theoretical basis to support an effect on CRDs. The attention-control group will also involve 4 in-home visits in mid morning and up to 4 brief telephone education sessions in the evening. Each session is prescriptive and designed to maximize attention; yet, sessions will not involve any of the components of the timed planned activity (e.g. meaningful activities or relaxation). The attention control group will receive printed Alzheimers Association and NIH materials on home modification, health promotion/ talking to your doctor and advanced care planning that coincide with session content. In Session 1 (home visit), the attention control interventionist will explain the nature of the visit and provides information on home safety. In Sessions 2-3 (one home visit and one phone call) the interventionist will work together with CG to answer questions about home safety and review health promotion material. In Sessions 4-5 (one home visit and one phone call), the interventionist will provide and review information on advanced care planning. Session 6 is a wrap up and review provided in the home. Time with the attention-control RA will be documented on a tracking sheet for each session and signed by the CG. Bi-monthly supervisory sessions with attention-control RAs will involve case presentations to track content of the attention-control sessions. In our previous studies, we found that the attention-control intervention is well received and that participants fully participated in sessions. Treatment Implementation Monitoring: We have a well-defined oversight plan of treatment implementation in both treatment and attention control group arms using the NIH Behavior Change Consortium. To enhance fidelity, we incorporate their recommended strategies including use of treatment manuals, regular contact of PI with interventionists who present cases and discuss protocol issues, and on-going monitoring through direct observation of randomly selected sessions. We will address fidelity through training (using intervention manuals and separate interventionists for each condition), delivery (reminder calls to CGs the night before the intervention sessions, records of home sessions by date and duration, receipt (checklist completed by study team regarding intervention engagement) and enactment (demonstration by CG to interventionists). Feedback will be provided to each interventionist throughout the study period. We will quantitatively evaluate treatment delivery, including dose, intensity; and treatment receipt. Biweekly supervisory sessions will be held with treatment interventionists and control group interventionists separately. All project staff will undergo extensive training before they have contact with subjects. We will audiotape 10% of treatment and 10% of control group sessions. Audiotapes will be reviewed by the research team using monitoring checklists that evaluate quality of the session. Table 1 (uploaded) describes the variables to be measured their respective testing occasions and sources.

**The following documents are currently attached to this item:**

*There are no documents attached for this item.*

**Deception**

Does your project use deception?

No

**International Research**

Are you conducting research outside of the United States?

No

**Analysis Plan**

Sample Size: Sample size calculations are based on our ability to detect a medium effect size (d) of 0.45; and d) a type I error rate of .05. Our projected effect size is justified for two reasons. First, clinical trials on symptoms of CRD use this effect size as an indication of clinical significance. Second we were able to achieve large treatment effects across outcomes in the pilot phase- although we acknowledge that effect sizes may be overly optimistic in pilot studies. To attain 80% power for a two-sided comparison of the two treatment groups at 1 month will require 78 dyads per group (Aim 1 and 2). We plan to recruit an additional 22 per group or 100 dyads for a total of 200 allowing for 22% attrition by 4 months (Aim 3). The statistical power for secondary analyses at 3 months will be the same as for the primary; 80% for a 0.45 effect size with 5% two-tailed tests. Analysis of aims: First, we will conduct

descriptive analyses and univariate comparisons of the experimental and control intervention group conditions. We will use Chi-square, Wilcoxon rank-sum tests, and independent groups t-tests as appropriate to identify any differences between experimental and control group participants at baseline. In addition to serving as a final data quality check, these analyses will be used to characterize our study population, assess the success of randomization in balancing the two groups and determine the impact of any dropouts on group balance. Aim 1: to test the timed activity intervention on patient CRD symptoms and QOL. Our primary analysis will examine the effect of the timed intervention compared to the attention control condition based on "intention to treat" (ITT). Data from all dyads randomized to the experimental group will be part of analyses regardless of actual number of completed intervention sessions. We will test the normality assumption for the primary CRD outcome measure (WASO) and for the other dependent measures (TST, neuropsychiatric symptoms; QoL) by examining the distribution of residuals after standard parametric comparisons. If the residual distribution is markedly skewed, we will examine whether data transformations are sufficient for improving the fit of the data to the normality assumption. Aim 1: To analyze the effects of the timed intervention on our primary outcomes difference scores (T2-T1) will be calculated for each participant and these change scores will be analyzed as a function of the treatment group, with the baseline observation (T1) serving as a covariate. Other potential covariates measured at baseline (e.g., age, education) will also be evaluated as potential predictors of change in outcome, and included as additional covariates of the intervention effect as indicated. Aim 2: To test the effect of the timed activity intervention on caregiver outcomes. For Aim 2, we follow the approach for Aim 1 by examining group differences in the baseline-adjusted change scores (T2-T1; T3-T1) for CG outcome measures of burden and intent to institutionalize. Aim 3: To test the mediating effect of patient HPA axis activity on symptoms of CRD. We will test mediation by modeling the measures of baseline-adjusted changes in CRD symptoms (WASO, TST, neuropsychiatric symptoms) in nested analytic models that either do or do not include the proposed mediator (T2-T1 change in saliva cortisol). Using nested regression models, estimates will be obtained of 1) the effect of the intervention on baseline-adjusted change in cortisol, 2) the effect of the change in cortisol on baseline-adjusted change in WASO (or other outcomes), 3) the effect of the intervention on baseline-adjusted WASO before adding change in cortisol to the model, and 4) the effect of the intervention on baseline-adjusted WASO after adding change in cortisol to the model. These path estimates are often referred to by the letters a, b, c, and c' in the mediation literature. The product of the a and b estimates (a\*b) represents the mediated effect, and this will be tested for statistical significance using the standard Sobel method or with bootstrapping techniques. The proportion of the total effect (c) that is explained by mediation (a\*b) will also be calculated and tested for significance. Mediation models for data from two-wave randomized trials can provide substantially different results depending on whether change scores are used and whether baseline covariate adjustments are implemented. Our approach will capitalize on this recent methodological work and provide sensitive analyses that determine whether the interventions impact on 1-month change in CRD symptoms is partly due to its effect on 1-month change in cortisol secretion.

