Once eligibility is determined and consent is signed, dyads of persons with dementia and their caregivers will receive a baseline home interview (T1). Following the baseline interview, participants will be randomly assigned to experimental or attention-control group conditions. Experimental dyads will receive up to 8 contacts with a interventionist over 1-month. The attention-control group dyads will receive comparable attention in a structured program involving the same number and mix of in-home and telephone contact as the treatment group. All dyads will be retested at 1-month from baseline (T2) to evaluate proximal outcomes of neuropsychiatric symptoms, QOL, and sleep quality and at 4 months (T3) to evaluate sustained uptake and distal outcomes of QOL and other measures of satisfaction with the study procedures. Outcome measures will be assessed by interviewers masked to treatment assignment. In addition, participants will be asked about their experience with the COVID-19 pandemic (using the University of Pittsburgh COVID Caregiving Questionnaire) at T3. This data will be collected via telephone only. The only information collected will include their answers to the questions on the survey and their de-identified participant number.

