## Objectives

### Overall objectives

We propose a definitive Phase III efficacy trial of the Healthy Patterns intervention, designed to improve sleep disturbance symptoms and QOL, that systematically builds on our pilot work demonstrating feasibility, safety and potential benefits. We will use a randomized, two-group, parallel design of 200 persons with dementia (PWD) and their family caregivers (dyads) assigned to the Healthy Patterns intervention or an attention control intervention of equivalent in-home attention and social contact. Specific components of this brief, one-month, eight session, home-based intervention include: 1) assessing PWD health/functional status and preferences/interests; 2) educating caregivers on environmental cues to promote activity and sleep; and 3) training of CG in using timed morning, afternoon, and evening activities based on circadian needs across the day. The patient focused outcomes of interest are QOL, and indices of sleep as measured by objective and subjective indicators including actigraphy, subjective sleep quality, and assessment of neuropsychiatric symptoms. Caregiver outcomes of interest are QOL, burden, confidence using activities, and sleep disruption. The specific aims for this study are to test: 1. The immediate (at 1 month) and sustained (at 4 months) effect of the Healthy Patterns activity intervention on PWD quality of life and CRD symptoms. Hypothesis 1a. Compared to control group participants, PWD receiving the intervention will demonstrate quality of life, total sleep time, nocturnal wake after sleep onset, day/night sleep ratio, and neuropsychiatric symptoms at 1 month. Hypothesis 1b. Compared to control group participants, PWD subjects receiving the intervention will demonstrate quality of life, total sleep time, and neuropsychiatric symptoms at 4 months. 2. The immediate (1 month) and sustained (4 months) effect of the Health Patterns activity intervention on caregiver outcomes. Hypothesis 2a. Compared to control group participants, caregivers who have received the intervention training will demonstrate quality of life, burden, confidence in using activities, and sleep disruption at 1 month. Hypothesis 2b. Compared to control group participants, caregivers who have received the intervention training will demonstrate quality of life, burden, confidence in using activities, and sleep disruption at 4 months. 3. The mediating effect of neuroendocrine activity on changes in CRD symptoms. Hypothesis 3. CRD symptoms will be mediated by changes in diurnal cortisol from baseline to 1 month.

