
### Primary outcome variable(s)

Symptoms of sleep disruption as measured by actigraphy Neuropsychiatric symptoms

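### The 4-month caregiver contrast drops dyads lost after T2 and ignores their T2 values; if that loss depends on T2 response differently by arm, the contrast is modestly biased

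*Combined protocol and SAP*

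**What the plan says.** All dyads are "retested at 1-month from baseline (T2) to evaluate proximal outcomes of neuropsychiatric symptoms, QOL, and sleep quality and at 4 months (T3", according to Administration of Surveys and/or Process.

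For Aim 1 the Analysis Plan writes one model: the T2-T1 change on treatment group, with T1 as covariate. It is labelled intention to treat, but the explanation concerns only how many sessions were completed. Aim 2 follows the same approach "by examining group differences in the baseline-adjusted change scores (T2-T1; T3-T1) for CG outcome measures of burden and intent to institutionalize".

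Dropouts appear in the analysis text only because the descriptive comparisons are meant to "determine the impact of any dropouts on group balance". Recruitment is set at 100 dyads per group "for a total of 200 allowing for 22% attrition by 4 months (Aim 3". No imputation, likelihood or mixed model, weighting or missing-data sensitivity analysis appears. The sample-size text adds: "The statistical power for secondary analyses at 3 months will be the same as for the primary". I read this as the T3 visit, which is elsewhere placed at 4 months.

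Two hypotheses concern 4 months. Hypothesis 2b says "caregivers who have received the intervention training will demonstrate quality of life, burden, confidence in using activities, and sleep disruption at 4 months". Of those four outcomes only burden is in the Aim 2 sentence. Hypothesis 1b says "PWD subjects receiving the intervention will demonstrate quality of life, total sleep time, and neuropsychiatric symptoms at 4 months", and no 4-month analysis of patient outcomes is written.

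**The concern.** The plan never uses the term complete cases. The exclusion follows from the chosen endpoint: without T3 there is no T3-T1 difference. A dyad seen at T2 and then lost therefore stays in the 1-month contrast and leaves the 4-month one.

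Suppose poorer responders leave mainly the experimental arm. The completers of that arm then look better at T3 than the randomised arm would have, and the contrast favours the intervention. If better responders leave that arm, or poorer responders leave the control arm, it goes against the intervention. Enlarging the sample for attrition protects precision, not validity.

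At stake is the claim of a sustained caregiver effect. The T2 values that would protect it are already collected.

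**Working it through.** **The plan's own figures.** For d = 0.45, two-sided 0.05 and 80% power, n = 2 × (1.960 + 0.842)² / 0.45² = 77.5, so 78 per group. Allowing for attrition, 78 / (1 − 0.22) = 100 per group. Both reproduce. The expected loss is 0.22 × 200 = 44 dyads, not split before and after T2.

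**Assumptions (not in the documents).** Outcomes are normal with SD 1 and higher is better. Correlations are T1-T2 0.6, T2-T3 0.6 and T1-T3 0.5. Loss is 22% in each arm. Selection b is the log-odds of loss per SD of poorer T2 value.

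**Hand check.** If only one arm is selected, the completers' baseline-adjusted bias is approximately

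bias ≈ (r23 − r12 × r13) × b × E[p(1 − p)] / (1 − loss),

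where p is the probability of loss after T2. The first factor is 0.6 − 0.6 × 0.5 = 0.30. By numerical integration over a standard normal T2, E[p(1 − p)] is 0.159, 0.148 and 0.128 for b = 0.7, 1.0 and 1.5.

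- b = 0.7: 0.30 × 0.7 × 0.159 / 0.78 = 0.043 SD
- b = 1.0: 0.30 × 1.0 × 0.148 / 0.78 = 0.057 SD
- b = 1.5: 0.30 × 1.5 × 0.128 / 0.78 = 0.074 SD

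For b = 0.5, E[p(1 − p)] is 0.165 and the bias is 0.30 × 0.5 × 0.165 / 0.78 = 0.032. A difference of 1.0 against 0.5 therefore gives 0.057 − 0.032 = 0.025 SD.

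**Simulation.** 12,000 trials per row, 100 per arm, no true effect. The 95% Monte Carlo error is about 0.0025 SD on bias and 0.4 points on rejection. The planned test is the ANCOVA of T3-T1 on group and T1.

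| Loss | Selection, experimental / control | Bias (SD) | Type I error |
|---|---|---|---|
| 22% after T2 | 0.7 / 0 | +0.042 | 6.3% |
| 22% after T2 | 1.0 / 0 | +0.057 | 7.0% |
| 22% after T2 | 1.5 / 0 | +0.076 | 8.0% |
| 22% after T2 | 0 / 1.0 | −0.059 | 7.2% |
| 22% after T2 | 0.7 / 0.35 | +0.019 | 5.5% |
| 22% after T2 | 1.0 / 0.5 | +0.025 | 5.2% |
| 22% after T2 | 1.5 / 1.0 | +0.017 | 5.1% |
| 22% after T2 | 1.0 / 1.0 | 0.000 | 5.1% |
| 11% before at random, 11% after | 0.7 / 0 | +0.023 | 5.4% |
| 11% before at random, 11% after | 1.0 / 0 | +0.033 | 5.5% |
| 11% before at random, 11% after | 1.5 / 0 | +0.044 | 6.1% |
| 11% before at random, 11% after | 1.0 / 0.5 | +0.014 | 5.2% |

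The standard error of the contrast is about 0.14 SD. Correlations of 0.5/0.5/0.4 and 0.7/0.7/0.6 (in the order T1-T2, T2-T3, T1-T3) change the 1.0 / 0 row only to 0.056 and 0.054.

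**Direction.** If better responders leave the experimental arm (b = −1.0), the bias is −0.056 SD.

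**With a true effect of 0.45.** With loss fixed at 22% in each arm, the planned contrast averages 0.506, 0.475 and 0.449 for selection 1.0/0, 1.0/0.5 and 1.0/1.0. If one common dropout rule acts in both arms (22% overall), it averages about 0.43 (b = 1.0) and 0.42 (b = 1.5).

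**The alternative.** For loss that occurs only at later visits, the likelihood estimate combines T2 on T1 and group (all dyads with T2) with T3 on T1, T2 and group (completers). Under no effect it is within 0.002 SD of zero in every row, with type I error of 4.7% to 5.2%. With the true effect it averages 0.448 to 0.449. Its precision gain is small (variance ratio 1.01 to 1.05).

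**Its limit.** If loss in one arm depends on the unseen T3 change (b = 1.0), the planned contrast is off by about 0.15 SD and the likelihood model still by about 0.12.

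**The case against.** The effect is small. A clearly raised type I error needs strong selection in one arm, none in the other, and most of the loss after T2. For partial differences, two of the three simulated error rates cannot be told from 5%. The documents give no dropout by arm or by timing. All of this stands, and it limits the point to a modest one.

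Scope also needs care. The written T3-T1 analysis covers only caregiver burden and intent to institutionalize, and Hypothesis 2b lists only the first. A reader might infer that the 4-month patient results of Hypothesis 1b are biased too. The documents do not support that: no 4-month patient analysis is written, so the gap there is an unspecified method. Which outcomes are measured at T3 can be verified only in part, because Study Procedures refers to an uploaded Table 1 that is not in the text.

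Three more stronger readings are tempting.

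- That the primary result is at risk. The primary outcomes, "Symptoms of sleep disruption as measured by actigraphy" and neuropsychiatric symptoms, are analysed as T2-T1, which loss after T2 does not touch.
- That the inflation is large. Opposite selection in the two arms (1 and −1) would give about 0.12 SD and a type I error of 13.7%, but nothing in the documents points to that pattern.
- That equal selection is always harmless. It is under no true effect, or with equal loss in each arm; under one common rule with a true effect there is slight attenuation.

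Finally, a likelihood model is no general cure. It assumes missing at random given T1, T2 and arm. It leaves most of the bias if loss depends on T3 itself, does not correct loss before T2 that depends on the unseen T2, and implicitly extrapolates outcomes beyond death, which Data and Safety Monitoring names as a possible event.

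**Conclusion.** The point holds in a conditional and limited form. As written, the 4-month contrast for caregiver burden and intent to institutionalize excludes dyads lost after T2, ignores their T2 values and has no missing-outcome method. It is biased if loss after T2 depends on T2 response differently by arm. The documents do not show whether that is so, nor in which direction.

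Under the stated assumptions, with all 22% lost after T2, the bias is about 0.04 to 0.08 SD (type I error 6% to 8%) for selection in one arm only, and about 0.02 to 0.03 SD (near 5%) for partial differences. It is smaller if part of the loss comes before T2. Against the planning effect of 0.45, the 1.0 / 0 case is 0.057 / 0.45 = 13%. The 1-month primary contrast and the sample-size arithmetic for 200 dyads are not at fault. The change is worth making because it is cheap and uses data already collected.

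**What to change.** - Estimate the 4-month contrast for caregiver burden, and for any other continuous outcome measured at T1, T2 and T3, from one likelihood-based repeated-measures model on all randomised dyads, with baseline adjustment, group-by-visit terms and unstructured covariance.
- State the scale of intent to institutionalize. If it is not continuous, use multiple imputation that includes T2.
- Use the same model for the Hypothesis 1b patient outcomes measured at T3.
- Keep the T2-T1 ANCOVA as the primary 1-month analysis.
- Add one prespecified control-based multiple-imputation sensitivity analysis, and report deaths separately by arm.
- Separately, reconcile Hypothesis 1b, which lists total sleep time at 4 months, with Study Instruments, where the actigraph comes off at 1 month. The model cannot supply a measurement that was not taken.

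The cost is analysis-plan wording and some programming, with no new data. The form reports 170 enrolled and 35 in follow-up only, so up to 170 − 35 = 135 may already be past T3 or lost. The rule should therefore be fixed before T3 data are unblinded or analysed, and its date recorded. The remaining weakness is the missing-at-random assumption, which the sensitivity analysis probes but does not remove.
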